## **4.2 Secondary Objective and Endpoints**

The secondary objective of this study is to describe the safety and tolerability of mirikizumab in healthy participants.

The secondary endpoints of this study are:

- Treatment emergent adverse events
- Serious adverse events (SAEs)

## **4.3 Exploratory Objectives and Endpoints**

The exploratory objectives and endpoints for this study are:

- To evaluate the effect of mirikizumab delivery device on immunogenicity
  - Treatment-emergent antidrug antibody (TE ADA)
- To evaluate the impact of injection-site location on PK
  - $C_{max}$
  - $AUC (0-\infty)$
  - $AUC(0-t_{last})$

## **5. STUDY DESIGN**

Study AMBW is a Phase 1, open-label, 2-arm, randomized, parallel-design, single-dose, multi-site study in healthy participants. At screening, participants will be stratified into 1 of 3 weight categories (less than 70 kg, 70 to 80 kg, and more than 80 kg).

Eligible participants will be admitted to the clinical research unit (CRU) on Day -1.

Within the 3 weight categories, participants will be randomized using a computer-generated allocation code:

- 1:1 to delivery device (either PFS [reference] or AI [test])
- within each delivery-device group 1:1:1 to injection site (abdomen, arm, or thigh)

On Day 1, participants will receive a  $2 \times 1$  mL (total 200 mg mirikizumab) SC dose delivered via the device and in the location assigned by the randomization.

Participants may be allowed to leave the CRU after completing the 4-hour safety assessments on Day 1, or later at the investigator's discretion, and will return for PK and immunogenicity sampling and safety assessments at predefined times up to 12 weeks postdose. Participants will be monitored for safety between outpatient visits by way of telephone assessment.

Safety and tolerability will be assessed through clinical laboratory tests, vital sign measurements, recording of AEs, physical examination, and immunogenicity.

## 6. TREATMENTS

The following is a list of the study treatment abbreviations that will be used in the TFLs.

Study Treatment Name	Injection Site	Abbreviation	Treatment order in TFL
200 mg Mirikizumab 2 x 1-mL (100 mg/mL) PFS (Reference)	Abdomen	Reference (Abdomen)	1
	Arm	Reference (Arm)	2
	Thigh	Reference (Thigh)	3
200 mg Mirikizumab 2 x 1-mL (100 mg/mL) AI (Test)	Abdomen	Reference (Abdomen)	4
	Arm	Reference (Arm)	5
	Thigh	Reference (Thigh)	6

## 7. SAMPLE SIZE JUSTIFICATION

Up to approximately 240 participants may be enrolled so that approximately 216 participants (108 in the PFS [reference] group and 108 in the AI [test] group) complete the study.

A sample size of 108 participants per treatment group will provide approximately 90% power that the 90% confidence interval (CI) of the geometric mean ratio of  $C_{max}$  and AUC between groups will fall within equivalence range of 0.8 to 1.25. This sample size calculation was based on the assumptions that the PK parameters have log-normal distribution, the percent coefficients of variation (CV%) of  $C_{max}$  and AUC are approximately 40% (based on previous trials), the expected ratio of geometric means is 1.07, and the CV% are the same for participants from each treatment group.

Participants who are randomized but not administered treatment, and participants who do not complete PK sampling through Day 85, may be replaced to ensure that approximately 216 participants (108 in each group) complete the study.

## 8. DEFINITION OF ANALYSIS POPULATIONS

The “Enrolled” population will consist of all participants randomly assigned to the study intervention (mirikizumab).

The “Safety” population will consist of all participants randomly assigned and who received study intervention (mirikizumab). Participants will be analyzed according to the intervention they actually received.

The “Pharmacokinetic” population will consist of all enrolled participants who receive a full dose of study intervention (mirikizumab) and have evaluable PK data.

All protocol deviations that occur during the study will be considered for their severity/impact and will be taken into consideration when participants are assigned to analysis populations.

## **9. STATISTICAL METHODOLOGY**

### **9.1 General**

Data listings will be provided for all data that is databased. Summary statistics and statistical analysis will only be presented for data where detailed in this SAP. For continuous data, summary statistics will include the arithmetic mean, arithmetic standard deviation (SD), median, minimum, maximum and N; for log-normal data (e.g. the PK parameters: AUCs and  $C_{max}$ ) the geometric mean and geometric CV% will also be presented. For categorical data, frequency count and percentages will be presented. Data listings will be provided for all participants up to the point of withdrawal, with any participants excluded from the relevant population highlighted. Summary statistics and statistical analyses will generally only be performed for participants included in the relevant analysis population. For the calculation of summary statistics and statistical analysis, unrounded data will be used.

Mean change from baseline is the mean of all individual participants' change from baseline values. Each individual change from baseline will be calculated by subtracting the individual participant's baseline value from the value at the timepoint. The individual participant's change from baseline values will be used to calculate the mean change from baseline using a SAS procedure such as Proc Univariate.

Data analysis will be performed using SAS® Version 9.4 or greater.

### **9.2 Demographics and Participant Disposition**

Participant disposition will be summarized and listed. The demographic variables age, sex, race, ethnicity, country of enrolment, site ID, body weight, height and body mass index will be summarized by treatment, and listed. All other demographic variables will be listed only.

### **9.3 Pharmacokinetic Assessment**

#### **9.3.1 Pharmacokinetic Analysis**

Noncompartmental methods applied with a validated software program (WinNonlin Phoenix v8.1 or later) to the serum concentrations of LY3074828 will be used to determine the following PK parameters, when possible:

Parameter	Units	Definition
AUC(0-t last )	µg*day/mL	area under the concentration versus time curve from time zero to time t, where t is the last time point with a measurable concentration
AUC(0-∞)	µg*day/mL	area under the concentration versus time curve from time zero to infinity
%AUC(t last -∞)	%	percentage of AUC(0-∞) extrapolated
C max	µg/mL	maximum observed drug concentration
t max	day	time of maximum observed drug concentration
t 1/2	day	half-life associated with the terminal rate constant ( $\lambda_z$ ) in non-compartmental analysis
CL/F	L/day	apparent total body clearance of drug calculated after extra-vascular administration
V Z/F	L	apparent volume of distribution during the terminal phase after extra-vascular administration
V ss/F	L	apparent volume of distribution at steady state after extra-vascular administration

Additional PK parameters may be calculated, as appropriate. The software and version used for the final analyses will be specified in the CSR. Any exceptions or special handling of data will be clearly documented within the CSR.

Formatting of tables, figures and abbreviations will follow the Eli Lilly Global PK/PD/TS Tool: NON-COMPARTMENTAL PHARMACOKINETIC STYLE GUIDE. The version of the tool effective at the time of PK analysis will be followed.

### General PK Parameter Rules

- Actual sampling times will be used in the final analyses of individual PK parameters, except for non-bolus predose sampling times which will be set to zero.
- Cmax and tmax will be reported from observed values. If Cmax occurs at more than one timepoint, tmax will be assigned to the first occurrence of Cmax.
- AUC parameters will be calculated using a combination of the linear and logarithmic trapezoidal methods (linear-log trapezoidal rule). The linear trapezoidal method will be applied up to tmax and then the logarithmic trapezoidal method will be used after tmax. The minimum requirement for the calculation of AUC will be the inclusion of at least three consecutive plasma concentrations above the lower limit of quantification, with at least one of these concentrations following Cmax. The AUC(0-∞) values where the percentage of the total area extrapolated is more than 20% will be flagged. Any AUC(0-∞) value excluded from summary statistics will be noted in the footnote of the summary table.
- Half-life (t1/2) will be calculated, when appropriate, based on the apparent terminal log-linear portion of the concentration-time curve. The start of the terminal elimination phase for each participant will be defined by visual inspection and generally will be the first point at which there is no systematic deviation from the log-linear decline in plasma

concentrations. Half-life will only be calculated when a reliable estimate for this parameter can be obtained comprising of at least 3 data points. If  $t_{1/2}$  is estimated over a time window of less than 2 half-lives, the values will be flagged in the data listings. Any  $t_{1/2}$  value excluded from summary statistics will be documented in the footnote of the summary table.

- A uniform weighting scheme will be used in the regression analysis of the terminal log-linear portion of the concentration-time curve.
- The parameters based on observed last quantifiable drug concentration ( $C_{last}$ ) will be reported.

### **Individual PK Parameter Rules**

- Only quantifiable concentrations will be used to calculate PK parameters except for special handling of certain concentrations reported below the lower limit of quantification (BQL). Plasma concentrations reported as BQL will be set to a value of zero when all the following conditions are met:
  - The compound is non-endogenous.
  - The samples are from the initial dose period for a participant or from a subsequent dose period following a suitable wash-out period.
  - The time points occur before the first quantifiable concentration.
- All other BQL concentrations that do not meet the above criteria will be set to missing.
- Also, where two or more consecutive concentrations are BQL towards the end of a profile, the profile will be deemed to have terminated and therefore any further quantifiable concentrations will be set to missing for the calculation of the PK parameters unless it is considered to be a true characteristic of the profile of the drug.

### **Individual Concentration vs. Time Profiles**

- Individual concentrations will be plotted utilizing actual sampling times.
- The terminal point selections will be indicated on a semi-logarithmic plot.

### **Average Concentration vs. Time Profiles**

- The average concentration profiles will be graphed using scheduled (nominal) sampling times and arithmetic average concentrations.
- The predose average concentration for single-dose data from non-endogenous compounds will be set to zero. Otherwise, only quantifiable concentrations will be used to calculate average concentrations.

- Concentrations at a sampling time exceeding the sampling time window specified in the protocol, or  $\pm 10\%$ , will be excluded from the average concentration profiles.
- Concentrations excluded from the mean calculation will be documented in the CSR.
- A concentration average will be plotted for a given sampling time only if 2/3 of the individual data at the time point have quantifiable measurements that are within the sampling time window specified in the protocol or  $\pm 10\%$ . An average concentration estimated with less than 2/3 but more than 3 data points may be displayed on the mean concentration plot if determined to be appropriate and will be documented within the CSR.

### **Treatment of Outliers during PK Analysis**

Application of this procedure to all PK analyses is not a requirement. Rather, this procedure provides justification for exclusion of data when scientifically appropriate. This procedure describes the methodology for identifying an individual value as an outlier for potential exclusion but does not require that the value be excluded from analysis. The following methodology will not be used to exclude complete profiles from analysis.

#### Data within an Individual Profile

A value within an individual profile may be excluded from analysis if any of the following criteria are met:

- For PK profiles during multiple dosing, the concentration of the predose sample exceeds all measured concentrations for that individual in the subsequent post-dose samples.
- For PK profiles during single dosing of non-endogenous compounds, the concentration in a predose sample is quantifiable.
- For any questionable datum that does not satisfy the above criteria, the profile will be evaluated, and results reported with and without the suspected datum.

#### Data between Individual Profiles

1. If  $n < 6$ , then the dataset is too small to conduct a reliable range test. Data will be analyzed with and without the atypical value, and both sets of results will be reported.
2. If  $n \geq 6$ , then an objective outlier test will be used to compare the atypical value to other values included in that calculation:
  - a. Transform all values in the calculation to the logarithmic domain.
  - b. Find the most extreme value from the arithmetic mean of the log transformed values and exclude that value from the dataset.

- c. Calculate the lower and upper bounds of the range defined by the arithmetic mean  $\pm 3*SD$  of the remaining log-transformed values.
- d. If the extreme value is within the range of arithmetic mean  $\pm 3*SD$ , then it is not an outlier and will be retained in the dataset.
- e. If the extreme value is outside the range of arithmetic mean  $\pm 3*SD$ , then it is an outlier and will be excluded from analysis.

If the remaining dataset contains another atypical datum suspected to be an outlier and  $n \geq 6$  following the exclusion, then repeat step 2 above. This evaluation may be repeated as many times as necessary, excluding only one suspected outlier in each iteration, until all data remaining in the dataset fall within the range of arithmetic mean  $\pm 3*SD$  of the log-transformed values.

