#### Reporting of Excluded Values

Individual values excluded as outliers will be documented in the CSR. Approval of the CSR will connote approval of the exclusion.

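### The SAP leaves open whether its 3-SD outlier rule can remove Cmax and AUC values from the primary bioequivalence model, and it promises no full-data result there

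*SAP*

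**What the plan says.** SAP 9.3.1, under Treatment of Outliers during PK Analysis, makes the procedure optional. It states that "this procedure provides justification for exclusion of data when scientifically appropriate" and that the method "does not require that the value be excluded from analysis". It adds that the method will not be used to drop complete profiles.

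Under Data between Individual Profiles, item 1 covers fewer than six values: "Data will be analyzed with and without the atypical value, and both sets of results will be reported". Item 2 covers six or more. The test is to "compare the atypical value to other values included in that calculation", using the mean ± 3 SD of the remaining log values. By step 2e a value outside that range is an outlier, "then it is an outlier and will be excluded from analysis". The test may be repeated without limit while at least six values remain.

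For a doubtful point inside one profile, Data within an Individual Profile promises "results reported with and without the suspected datum". Under Reporting of Excluded Values, exclusions are documented in the clinical study report (CSR), and "Approval of the CSR will connote approval of the exclusion".

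SAP 9.3.2 sets out the primary model (device, location, weight stratum) and requires the 90% CI for all three parameters to lie within 0.8 to 1.25. It neither invokes the outlier procedure nor exempts the model from it. Protocol 9.4.2 has no outlier rule, and SAP 11 reports no change from the protocol.

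**The concern.** Two analysts could treat the same extreme Cmax differently and each cite the SAP: one keeps it because exclusion is not required, the other drops it under step 2e. No assay, sampling or dosing error is needed for removal, and there are no criteria for when exclusion is scientifically appropriate.

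The comparison set is also undefined. It could be all 216 values, one device group, one device-by-site cell, or only a descriptive summary.

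The promise to show both results stops where the study is decided. With 108 per device and 36 per device-by-site cell, every primary comparison has six or more values.

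An extreme value can be genuine. Protocol 2.2.5 reports a few participants whose antidrug antibody titers were high enough to affect exposure. The study is open-label and exclusion is discretionary, so a reader of the CSR could not rule out that the version was chosen after the result was seen.

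**Working it through.** **Inputs from the documents** (SAP 7 and 9.3.2; Protocol 9.2): 108 per device, CV 40%, log-normal data, expected ratio 1.07, limits 0.8 to 1.25, 90% CI, all three parameters required.

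**The plan's own figure.**
- Log-scale SD = √ln(1 + 0.4²) = 0.3853.
- SE of the device difference = 0.3853 × √(2/108) = 0.0524.
- Upper side: (ln 1.25 − ln 1.07)/0.0524 − 1.645 = 1.32. Lower side: (ln 1.07 − ln 0.8)/0.0524 − 1.645 = 3.90.
- Power = Φ(1.32) + Φ(3.90) − 1 = 90.7% (90.5% with the t distribution). The stated power of approximately 90% is reproduced.

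**Why the comparison set matters.** Take a true ratio of 1.25 and pool the devices.
- Each device mean lies ln(1.25)/2 = 0.112 from the overall mean. The pooled SD is √(0.3853² + 0.112²) = 0.401, so the cut-off is 3 × 0.401 = 1.203.
- A high AI value is removed beyond (1.203 − 0.112)/0.3853 = 2.83 SD of its own group, with probability about 0.0023.
- A low AI value is removed only beyond (1.203 + 0.112)/0.3853 = 3.41 SD, with probability about 0.0003.
- PFS values show the mirror image. Pooled testing therefore pulls the ratio slightly toward 1. Testing within device is symmetric and does not.

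**Simulation.** 216 participants, 12 per device × site × weight cell, no true site or weight effect (assumed). Steps 2a-2e were iterated separately for each parameter, followed by the SAP model. Mechanical application makes these figures upper bounds, because the SAP makes the procedure optional. True ratio at a limit (1.25 or 0.80):

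| Comparison set | False bioequivalence, per parameter | All three parameters* | Mean ratio when truth is 1.25 |
|---|---|---|---|
| Full data | about 5% | 2.2-2.5% | 1.250 |
| Pooled 216 | 6.5-6.9% | 2.8-3.3% | about 1.243 |
| Within device | about 5.5-5.9% | 2.5-2.9% | no shift |

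*Assumed correlations: Cmax-AUC 0.8, AUC-AUC 0.99. Neither is in the documents. Ranges cover both limits and repeated runs.

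- Within device-by-site cells, a run of 4,000 trials gave 6.0% per parameter against 5.3% on full data (Monte Carlo SE about 0.35 points).
- With pooled testing, at least one genuine value per parameter is removed in about 50% of trials, and the 90% CI narrows by about 1.4%.
- If the more favourable of the full-data and pooled-exclusion results could be chosen, the all-three rate would be 2.5-4.0% over Cmax-AUC correlations of 0.7 to 0.9.
- At a ratio of 1.07, per-parameter power is 90.5% on full data and 91.8% after pooled exclusion (40,000 trials). In the 4,000-trial run it was 90.7% on full data and 90.8% after within-device exclusion.

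**The case against.** The best defence is that the rule was never meant for the primary model. It sits in SAP 9.3.1 on parameter derivation, whereas the model is in 9.3.2. Nearby text speaks of values left out of mean profiles and summary statistics, so a descriptive reading fits at least as well as any other. This stands as a plausible reading. The SAP does not state it, so the ambiguity remains.

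There are real safeguards. The SAP is signed off before the first participant visit (SAP 3). All databased data are listed (9.1). Special handling and excluded values are documented in the CSR, and AUC(0-∞) values left out of summaries are footnoted (9.3.1). Someone holding the data could rebuild the full-data result. None of this commits the sponsor to report it.

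The bar on excluding complete profiles also helps. If it prevents one participant from losing all three values, the pooled all-three rate at correlation 0.8 is 2.8% rather than 3.2%, against 2.3% on full data (6,000 trials, ratio 1.25, Monte Carlo SE about 0.2 points). It does not clearly protect a single Cmax or AUC value.

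A with-and-without analysis is promised below six values because the range test is unreliable there, so its absence at six or more may be deliberate. That explains the wording but leaves the decisive analysis without a committed full-data result.

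Three stronger readings are tempting, and the documents do not support them:
- **That the SAP requires removal from the primary model.** The procedure is expressly optional, and its scope is unstated.
- **That the trial's false-positive rate exceeds 5%.** Under the plan's log-normal assumption it stays below 5% at trial level, even with the favourable choice. It reached 5.3% only with assumed t(5) tails at correlation 0.9.
- **That real extremes would cluster in one device and reverse the verdict.** In one illustration, 5% of AI participants have one-fifth exposure and the overall ratio sits at 0.80. Declared bioequivalence then goes from 5.2% to 33-43%. No document gives such a rate, and Protocol 2.2.5 says that most antibody-positive participants had low titers with no clear effect on exposure.

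**Conclusion.** The point holds as a minor one. The two statements on exclusion conflict, the reach of the rule and its comparison set are undefined, and no full-data bioequivalence result is promised for the comparison that decides the study. These are findings on the text and do not depend on the simulation.

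The numerical consequence is small and depends on the reading. The error increase is largest with pooled testing: up to about 1.9 points per parameter (5% to 6.9%) and about 1 point at trial level. It is smaller within device, and there is none if the rule governs only descriptive summaries. The sizes assume log-normal data with CV 40%, mechanical application and, at trial level, the correlations given above. The reason to act is transparency in an open-label study with a discretionary rule, at almost no cost.

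**What to change.** 1. In SAP 9.3.2, state that the primary bioequivalence analysis of Cmax, AUC(0-∞) and AUC(0-tlast) uses all evaluable values in the pharmacokinetic population, and that the between-profile 3-SD test removes none of them.
2. Allow removal from that analysis only for a documented assay, sampling or dosing error, decided before the device comparison is run.
3. Report any 3-SD-excluded result only as a labelled sensitivity analysis beside the full-data result, and name the set of values tested.
4. In 9.3.1, reword step 2e as a permission (*may be excluded*), so that it agrees with the opening of the procedure.

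Cost: a few sentences and one extra table. Compared with mechanical pooled exclusion, the CI is about 1.4% wider if genuine extremes occur, and per-parameter power is about 1.3 points lower (91.8% − 90.5%). Full-data power stays at the planned level of about 90% per parameter.

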#### Reporting of Excluded Values

Individual values excluded as outliers will be documented in the CSR. Approval of the CSR will connote approval of the exclusion.

### **9.3.2 Pharmacokinetic Statistical Methodology**

The  $C_{max}$ , AUC (0- $\infty$ ), and AUC(0- $t_{last}$ ), will be log-transformed and analyzed using a linear fixed-effects model. The model will include delivery device, injection location, and weight stratification as fixed effects. The dosing regimen differences between AI and PFS administrations will be back-transformed to present the ratios of geometric least squares means and the corresponding 90% CI.

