## 4.2. Scientific Rationale for Study Design

Conducting the study in healthy participants mitigates the potential confounding effects of the disease state and concomitant medications in participants with UC. A population of healthy participants is frequently used in the assessment of the PK of both small and large molecules.

Single doses of mirikizumab and the PK sampling time points have been selected to generate PK profiles sufficient to fulfill the study objectives.

Participants will be randomized to receive injections in the arm, thigh, or abdomen, as injection location has been observed to have an impact on bioavailability in some studies with mirikizumab.

Previous population PK analyses have shown that patients with a lower body weight tended to have a lower clearance and/or central volume of distribution. While the effects of body weight on these PK parameters were statistically significant, it was not considered to be clinically relevant. However, to mitigate these potentially confounding effects, approximately equal numbers of participants in each weight category are proposed to avoid a large difference in mean weight between the test and the reference delivery-device groups. A participant population of 72 per weight group is an approximate target with the recommended weight categories selected based on the distribution of weights in prior studies. The number of participants assigned to each delivery device and the number of participants assigned to each site of injection is desired to be balanced.

A parallel-group design is chosen because a crossover design is impractical for mirikizumab, which has a half-life of approximately 10.5 days. Additionally, a crossover study could confound PK data if participants develop neutralizing antidrug antibodies (ADAs).

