#### **Example SAS Code:**

```
proc mixed data=xxx;
by parameter;
class device location strat_weight;
model log_pk = device location strat_weight / residual;
lsmeans device / alpha=0.1 cl pdiff;
ods output lsmeans=lsmeans diff=diffs;
run;
```

The  $t_{max}$  of mirikizumab between the AI (Test) and PFS (Reference) administrations will be analyzed using a Wilcoxon rank sum test. Estimates of the median difference, 90% CIs, and p-values from the Wilcoxon rank sum test will be calculated.

Additional comparisons will be made between:

- The 2 delivery devices (AI [Test] versus PFS [Reference]) separately at each injection location (injection location will be removed from the model above)

- The 3 injection locations (arm [Test] versus abdomen [Reference] and thigh [Test] versus abdomen [Reference]) separately for each device (device will be removed from the model above)

The 2 delivery devices (AI [Test] versus PFS [Reference]) will be considered bioequivalent if the 90% CI of the ratio of geometric least squares means of  $C_{max}$ , AUC (0- $\infty$ ), and AUC(0- $t_{last}$ ) fall within 0.8 to 1.25. There would not be power in the model to achieve bioequivalence boundaries for any specific injection location, therefore the bioequivalence for the 3 injection locations will not be determined.

PK parameters may be normalized by body weight for summarizing data. Additional PK analyses may be conducted if deemed appropriate.

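### Prespecifying log screening weight beside the three weight strata would be a cheap, small precision gain; the planned primary model is valid as it stands

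*SAP*

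**What the plan says.** SAP 9.3.2 and Protocol 9.4.2.2 give the same primary model. In the SAP's words: "The model will include delivery device, injection location, and weight stratification as fixed effects". The example SAS code confirms it with "model log_pk = device location strat_weight / residual", where the weight variable is a CLASS factor. The categories are below 70 kg, 70 to 80 kg and above 80 kg. They are also the randomization strata, with a target of about 72 participants each (Protocol 4.1 and 4.2).

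Protocol 4.2 explains why weight matters: "Previous population PK analyses have shown that patients with a lower body weight tended to have a lower clearance and/or central volume of distribution". It adds that the effects were statistically significant but not regarded as clinically relevant. The strata are meant to keep mean weight similar in the two device groups.

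Weight is measured at screening (Protocol 1.3 and 8.2.1). As a number it appears in the SAP's PK methods only as an optional normalization for summaries, not in the inference.

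**The concern.** A three-level factor treats everyone in a stratum as having the same weight. The outer strata have no limit of their own; only the BMI criterion (Protocol 5.1) restrains them indirectly. If exposure falls with weight, the weight variation left inside the strata stays in the residual and widens the 90% CI on which bioequivalence is decided. A chance difference in mean weight between devices within a stratum also goes unadjusted. A baseline covariate would address both without new data.

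**Working it through.** **1. Reproducing the plan's power.** Inputs from SAP 7: "A sample size of 108 participants per treatment group will provide approximately 90% power that the 90% confidence interval (CI" lies in the limits ("between groups will fall within equivalence range of 0.8 to 1.25"), the CVs of Cmax "and AUC are approximately 40% (based on previous trials", and "the expected ratio of geometric means is 1.07". The CI level is set by "lsmeans device / alpha=0.1 cl pdiff".

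- SD of the log parameter = √ln(1 + 0.40²) = √0.1484 = 0.3853.
- SE of the device difference = 0.3853 × √(2/108) = 0.0524.
- Residual df with 216 completers and 6 parameters = 210; t(0.95, 210) = 1.652.
- CI half-width = 1.652 × 0.0524 = 0.0866 on the log scale.
- Power of the two one-sided tests at ratio 1.07, for one parameter = 90.5%. The plan says about 90%, so it reproduces.

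**2. What the strata leave over.** These inputs are assumptions, not from the documents: weight normal with mean 75 kg, SD 10, 13 or 16 kg, truncated to 45 to 115 kg, equal numbers per stratum. The within-stratum variance of log weight (W) is then 0.0039, 0.0058 and 0.0071. The strata already remove about 79% to 80% of the variance of log weight. Of what remains, 88% to 93% lies in the two outer strata.

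**3. Effect of adding log weight.** Take exposure proportional to weight^(−b), and 40% as the CV remaining after the strata.

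- R² within strata = b² × W / 0.1484.
- New half-width = t(0.95, 209) × 0.3853 × √(1 − R²) × √(2/108) × √(1 + 1/208). The last factor is the expected variance inflation from one added covariate.
- Chance imbalance, 1 SD on the log ratio = b × √(W × 2/108).

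| Weight SD, b | R² | Change in CI width | Power | Imbalance (1 SD) |
|---|---|---|---|---|
| 10 kg, 0.5 | 0.7% | −0.1% | 90.6% | 0.4% |
| 13 kg, 0.5 | 1.0% | −0.2% | 90.6% | 0.5% |
| 16 kg, 0.5 | 1.2% | −0.4% | 90.7% | 0.6% |
| 10 kg, 1.0 | 2.6% | −1.1% | 91.0% | 0.8% |
| 13 kg, 1.0 | 3.9% | −1.7% | 91.4% | 1.0% |
| 16 kg, 1.0 | 4.8% | −2.2% | 91.6% | 1.1% |

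**4. The downside.** With R² = 0, √(1 + 1/208) and the lost degree of freedom make the expected interval 0.24% wider, and power is 90.4%. Break-even R² is 1 − 1/(1 + 1/208), about 0.5%.

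**5. Single trials.** Simulation (3,000 trials per scenario) of the planned model with and without log weight covered both readings of the 40% CV: total, or residual after strata. The share of trials in which the interval came out wider with log weight was:

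- b = 0: 79% to 81%
- b = 0.3: 62% to 70%
- b = 0.5: 38% to 55%
- b = 0.75: 14% to 35%
- b = 1.0: 2% to 17%

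If 40% is the total CV, the mean narrowing at b = 1.0 reaches 2.8%.

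**The case against.** The strongest reply is that nothing here is broken. Protocol and SAP agree, the model adjusts for the factor used in randomization, and the stated power is reached without the extra term. Chance imbalance within strata is not bias under randomization. The planned 90% CI already allows for it, and one SD of about 0.004 to 0.011 is small against a half-width of 0.0866. Stratification serves the protocol's stated aim of similar mean weight by device, and the protocol judged the weight effect not clinically relevant. All of this stands, and it is why the point is only a suggestion. The remark on clinical relevance does not settle the matter, because a covariate can improve precision without being clinically important, but it does warn against expecting much.

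The second reply concerns the assumptions. The documents give the direction of the weight effect and no exponent, R² or weight distribution. An exponent range starting at 0.5 leaves out values near 0.3 or below, where the term is neutral or slightly harmful. That also stands, and the zero-effect case is shown above for this reason.

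A reader might infer that log weight brings tighter intervals at no cost. The documents do not support that: the cost is one degree of freedom and about 0.24% of expected width if weight explains nothing within strata, and no figure in them shows that the break-even R² is exceeded. A reader might also infer that the device comparison is biased or underpowered without the covariate. The design and the reproduced power contradict this.

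**Conclusion.** A minor, optional improvement. Weight is recorded before dosing, has a reported PK effect, and is used in the primary inference only in coarse form. The expected gain is about 0.1% to 2.2% of CI width and at most about one point of power (90.5% to 90.6–91.6%). This rests on the assumed weights (mean 75 kg, SD 10 to 16 kg), exponents of 0.5 to 1.0, and 40% as the CV after strata. The expected loss, if weight has no effect within strata, is about 0.24% of width. Narrowing in the actual trial is likely towards the upper exponents and close to even odds at 0.5. The bioequivalence conclusion should not be expected to turn on this choice.

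**What to change.** In SAP 9.3.2, add log(screening body weight) as a continuous term, outside the CLASS statement, beside device, location and weight stratum in the model for Cmax, AUC(0-∞) and AUC(0-tlast). Keep the stratum. If weight was repeated because enrollment fell outside the 28-day screening window (Protocol 5), name the last predose value, and never the Day 85 weight. Say whether the by-location and by-device models carry the same term.

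Fix this before SAP sign-off, which is due before the first participant visit (Protocol 9.4, SAP 3). If that visit has already occurred, keep the planned model as primary and report the log-weight model only as a sensitivity analysis, so that the primary model is not chosen after data exist.

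Cost: one line of model text and code, one of about 210 degrees of freedom, and no new data. SAP 11, which now reports no changes from the protocol, would have to record the change and its reason. The sponsor would also have to judge, under Protocol 9.4, whether it alters a principal feature and so needs an amendment.
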